## 9.8.2 Deaths and Serious Adverse Events

Subject incidence of the following will be tabulated by SOC, PT and maximum severity grade per CTCAT V4.03:

- serious treatment-emergent AEs

Sponsor: Amgen Inc.

Statistical Analysis Plan

Protocol No: 20130108

10-December-2018/ Version 2.0

---

Subject incidence of the following will be tabulated by preferred term in descending order of frequency of the ABP798 arm:

- serious treatment-emergent AEs
- treatment-emergent fatal AEs

A subject listing of SAEs and AEs with fatal outcome will be also provided.

### 9.8.3 Laboratory Data

Laboratory test results are reported in International System of Units (SI) units.

Laboratory values and change from baseline will be summarized using descriptive statistics at each analysis visit by treatment. Shift tables of the worst on-study laboratory toxicity based on CTCAE v4.03 grading relative to baseline will be presented by treatment group. The shift tables will take into account all post-baseline (scheduled and unscheduled) laboratory results for determination of worst on-study laboratory toxicity within the two summary timeframes listed previously. For labs with toxicity grading in two directions, for toxicity due to decreased value, the maximum grade is corresponding to the minimum post-baseline value. For toxicity due to increase value, the maximum grade is corresponding to the maximum post-baseline value. In addition, subject incidence tables and listings of grade  $\geq 3$  laboratory toxicities will be provided based on all post-baseline (scheduled and unscheduled) laboratory results for each of the two reporting periods. Standard ranges will be used for the laboratory analysis.

Lab assessments will be grouped for summary as follows:

- Hematology – white blood cell parameters: white blood cell count and differential
- Hematology – red blood cell parameters: hemoglobin, packed cell volume or hematocrit, red blood cell count, mean corpuscular hemoglobin, mean corpuscular hemoglobin concentration
- Hematology – other parameters: platelets
- Serum chemistry – hepatobiliary parameters: alanine aminotransferase (ALT), aspartate aminotransferase (AST), total bilirubin, alkaline phosphatase, gamma glutamyl transferase
- Serum chemistry – general chemistry: sodium, potassium, albumin, total protein, non-fasting glucose
- Serum chemistry – renal function tests: urea, creatinine

### 9.8.4 Vital Signs and Physical Examination

Observed and change from baseline in vital signs will be summarized by parameter and treatment. Descriptive statistics will be shown for baseline, each post-baseline time point up to EOS, and the change from baseline to each post-baseline time point.

Sponsor: Amgen Inc.

Statistical Analysis Plan

Protocol No: 20130108

10-December-2018/ Version 2.0

### 9.8.5 Immunogenicity

The number and percentage of subjects developing binding and neutralizing ADA will be tabulated by treatment .

Pre-existing antibody incidence and developing antibody incidence will be summarized. Pre-existing antibody is defined as a positive antibody result at baseline (see [Section 5.1](#) for definition of baseline). Developing antibody incidence is defined as a negative or no binding antibody result at baseline and a positive antibody result at a post-baseline time point. A transient antibody result is defined as a positive post-baseline result with a negative result at the subject's last time point tested within the study period.

In addition, the frequency and percent of subjects with positive binding or neutralizing ADA results will be tabulated by visit and treatment.

### 9.8.6 Methods for Handling Missing Data for Safety

Missing safety endpoints will not be imputed.

#### Imputation for Partial or Missing Dates

If dates are missing or incomplete for an AE (including deaths) or concomitant medication, the following algorithm will be used for imputation:

**Table 2. Imputation Rules for Partial or Missing Start Dates**

Start Date		Stop Date						
		Complete: yyyymmdd		Partial: yyyyymm		Partial: yyyy		Missing
<1 st dose	≥1 st dose	<1 st dose yyyymm m	≥1 st dose yyyymm	<1 st dose yyyy	≥1 st dose yyyy			
Partial : yyyy m	= 1 st dose yyyymm	2	1	n/a	1	n/a	1	1
	≠ 1 st dose yyyymm		2	2	2	2	2	2
Partial : yyyy	= 1 st dose yyyy	3	1	3	1	n/a	1	1
	≠ 1 st dose yyyy		3		3	3	3	3
Missing		4	1	4	1	4	1	1

**1** = Impute as the date of first dose

**2** = Impute as the first of the month

**3** = Impute as January 1 of the year

**4** = Impute as January 1 of the stop year

Note: If the start date imputation leads to a start date that is after the stop date, then there is a data error and do not impute the start date.

Imputation rules for partial or missing stop dates:

Sponsor: Amgen Inc.

Statistical Analysis Plan

Protocol No: 20130108

10-December-2018/ Version 2.0

1. Initial imputation
  - a. For partial stop date “mmyyyy”, impute the last of the month.
  - b. For partial stop date “yyyy”, impute December 31 of the year.
  - c. For completely missing stop date, do not impute.
2. If the stop date imputation leads to a stop date that is after the death date, then impute the stop date as the death date.
3. If the stop date imputation leads to a stop date that is before the start date, then there is a data error and do not impute the stop date.

Imputation rules for partial or missing death dates:

1. If death year and month are available but day is missing:
  - a. If “mmyyyy” for last contact date = “mmyyyy” for death date, set death date to the day after the last contact date.
  - b. If “mmyyyy” for last contact date < “mmyyyy” for death date, set death date to the first day of the death month.
  - c. If “mmyyyy” for last contact date > “mmyyyy” for death date, data error and do not impute.
2. If both month and day are missing for death date or a death date is totally missing, set death date to the day after the last contact date.

The imputed dates will be used to assess whether AEs should be considered as treatment-emergent and if medications should be included in the safety summaries as prior or concomitant, however the original, partial dates will be included in data listings.

## 9.9 EXPLORATORY ANALYSES

### 9.9.1 DAS28-CRP Individual Components

The DAS28-CRP individual components of swollen (28) and tender joint counts (28), subject's global health assessment, and CRP will be summarized as change from baseline descriptively by treatment and visit using the FAS as observed.

### 9.9.2 ACR Individual Components

The ACR individual components of swollen (66) and tender joint counts (68), subject's global health assessment, investigator's global assessment, subject's assessment of disease-related pain, HAQ-DI and CRP will be summarized descriptively by treatment and visit using the FAS as observed.

## 10. CHANGE FROM PROTOCOL SPECIFIED ANALYSIS

During the development of this document, pharmacokinetic concentration analysis set was defined in the SAP to better describe the analysis population criteria which will be the population set in the PK serum concentration TFLs. Additionally, the definition of per protocol and per protocol pharmacokinetic parameter analysis sets were modified to include “important protocol deviation” instead of “protocol deviation” to properly reflect the population included in this analysis set.

Sponsor: Amgen Inc.

Statistical Analysis Plan

Protocol No: 20130108

10-December-2018/ Version 2.0

---

Furthermore, per protocol analysis set criteria also includes the condition of 2 full infusion of the first dose, meaning that the drug compliance of 90%-110% of the first dose, additionally to ensure this analysis set follows the protocol requirements.

## 11. VALIDATION

The programming (including quality control) of the analysis datasets and TFLs will be conducted under PRA's standard processes PRS 050 and documented accordingly. The entire set of TFL will be checked for completeness and consistency prior to its delivery to the client by the lead statistician and a senior level statistician, or above, who is not a member of the project team.

The PRA validation process is repeated any time TFL are redelivered using different data. Execution of this validation process is documented through the study Table of Programs that is provided to the client at study conclusion.

**APPENDIX 1 GLOSSARY OF ABBREVIATIONS**

Glossary of Abbreviations:	
ACR	American College of Rheumatology
ACR20	20% Improvement in ACR Core Set Measurements
ACR50	50% Improvement in ACR Core Set Measurements
ACR70	70% Improvement in ACR Core Set Measurements
ADA	Anti-drug Antibody
ADaM	Analysis Data Model
AEOI	Adverse Event of Interest
AE	Adverse Event
ALT	Alanine Aminotransferase
AST	Aspartate Aminotransferase
AUC	Area Under the Curve
BMI	Body Mass Index
BQL	Below Quantifiable Limit
CCP	Anti-cyclic Citrullinated Peptide
CDAI	Clinical Disease Activity Index
CDISC	Clinical Data Interchange Standards Consortium
CI	Confidence Interval
CIOMS	Council for International Organizations of Medical Sciences
CL	clearance
C last	Last measurable Concentration
C max	Maximum Concentration
CRP	C-reactive Protein
CTCAE	Common Terminology Criteria for Adverse Events
CTMS	Clinical Trial Management System
CV	Coefficient of Variation
DAS	Disease Activity Score
DMARDs	Disease-modifying Anti-rheumatic Drugs
DMC	Data Monitoring Committee
eCRF	Electronic Case Report Form
EOI	End of Infusion
EOS	End of Study
EULAR	European League Against Rheumatism
FAS	Full Analysis Set
GEE	Generalized Estimating Equation
GH	General Health

Sponsor: Amgen Inc.

## Statistical Analysis Plan

Protocol No: 20130108

10-December-2018/ Version 2.0

GMR	Geometric Mean Ratio
HAQ-DI	Health Assessment Questionnaire Disability Index
IP	Investigational Product
IPD	Important protocol deviation
IXRS	Interactive Voice or Web Response System
IV	Intravenous
KM	Kaplan-meier
MedDRA	Medical Dictionary for Regulatory Activities
MRT	mean residence time
NCA	Noncompartmental techniques
NCI-US	National Cancer Institute
NSAID	Non-steroidal Anti-inflammatory Drug
PD	Pharmacodynamic
PD	Protocol Deviations
PK	Pharmacokinetic
PP	Per Protocol
PT	Preferred Term
Q1	25 th Percentile
Q3	75 th Percentile
RA	Rheumatoid Arthritis
RD	Risk Difference
RF	Rheumatoid Factor
RR	Risk Ratio
SAP	Statistical Analysis Plan
SAE	Serious Adverse Event
SDAI	Simplified Disease Activity Index score
SDTM	Standard Data Tabulation Model
SI	International System of Units
SJC28	Swollen Joint Count (28 Joints)
SMQ	Standardised MedDRA Query
SOC	System Organ Class
t 1/2	Terminal elimination half-life
TEAE	Treatment-emergent Adverse Event
TFL	Tables, Figures, and Listings
T max	Time to which the maximum serum concentration was observed
TJC28	Tender Joint Count (28 Joints)
TNF	Tumor Necrosis Factor

Sponsor: Amgen Inc.

Statistical Analysis Plan

Protocol No: 20130108

10-December-2018/ Version 2.0

VAS	Visual Analog Scale
WHO-DD	World Health Organization Drug Dictionary
$\lambda_z$	Terminal elimination rate constant

Sponsor: Amgen Inc.

Statistical Analysis Plan

Protocol No: 20130108

10-December-2018/ Version 2.0

---

## APPENDIX 2 METHOD FOR MISSING INDIVIDUAL COMPONENTS OF ACR CALCULATION

In the case of some ACR components are missing, the ACR composite scores will be based on the non-missing components. If a subject's non-missing components are not sufficient to identify ACR composite score, then that subject will be considered as missing ACR response. The corresponding algorithm is listed below (using ACR 20 as an example):

- If both Tender or Swollen Joint Counts are improved at least 20%, and
  - If three or more of the other five ACR components are improved at least 20%, the subject is an ACR 20 responder;
  - If three or more of the other five ACR components are not improved at least 20%, the subject is an ACR 20 non-responder;
  - If none of the above, the ACR response for the subject cannot be determined due to missing data and is therefore coded as missing.
- If either swollen or tender joint counts is not improved at least 20%, the subject is an ACR non-responder
- If either swollen or tender joint counts is missing and the other improved at least 20%,  
and
  - If three or more of the other five ACR components are not improved at least 20%, the subject is an ACR 20 non-responder;
  - Otherwise, the ACR response for the subject cannot be determined due to missing data and is therefore coded as missing

Sponsor: Amgen Inc.

Statistical Analysis Plan

Protocol No: 20130108

10-December-2018/ Version 2.0

## APPENDIX 3 METHOD FOR MISSING INDIVIDUAL JOINT ASSESSMENTS

A Pain/Tenderness or Swollen Joints may be coded as follows:

Joint Codes:	00 = None
	01 = Positive
	08 = Permanently inevaluable because of replaced, fused joint
	09 = Not evaluated because of intra-articular corticosteroid injection
	77 = Not Done

The missing individual joint assessments due to artificial/fused joint, intra-articular corticosteroid injection or not done for other reason are imputed as the followings:

For Joint Codes = 08,

- At Screening: Code as missing at current visit only
- At Baseline: Exclude the joint from the total joint counts for baseline and all subsequent visits.
- Post-Baseline (If a joint is coded as 08 at a post-baseline visit but not at baseline): Code as “01” (failed) beginning with the current visit and all visits subsequent to the current visit.

For Joint Codes = 09,

- At Screening: Code as “01” (failed) at current visit only
- At Baseline: Code as “01” (failed) for baseline and all subsequent visits.
- Post-Baseline: Code as “01” (failed) beginning with the current visit and all visits subsequent to the current visit.

For Joint Codes = 77,

- At Baseline: Code as missing and exclude the joint from the total joint counts for baseline.
- Post-baseline: Code as missing and exclude the joint from the total joint counts for the current visit.

If there are joints being excluded after above imputation, the Tender or Swollen Joint Counts will be prorated based on the algorithm described below.

Sponsor: Amgen Inc.

Statistical Analysis Plan

Protocol No: 20130108

10-December-2018/ Version 2.0

---

**Prorated Joint Counts**

If at least half but not all joints are evaluable (14 joints for the DAS28 joint counts, 34/33 for the 68/66 joint counts), then the observed prorated Tender or Swollen Joint Counts will be calculated. The prorated scores will be adjusted based upon the number of evaluable joints: the counted score will be multiplied by 28, 66, or 68 as applicable and divided by the number of joints evaluated. Otherwise, the Tender or Swollen Joint Counts is missing.

For example, if only 25 of the 28 DAS joints are assessed at a visit and 10 of those 25 are pain/tenderness and 8 of those 25 are swollen, the prorated joint counts are:

$$\text{Tender Joint Counts: } 10/25*28 = 11.20$$

$$\text{Swollen Joint Counts: } 8/25*28 = 8.96$$

That is, the values of 11.20 and 8.96 will be used in calculating the percent improvement, not the values of 10 and 8.

Sponsor: Amgen Inc.

Statistical Analysis Plan

Protocol No: 20130108

10-December-2018/ Version 2.0

---

## APPENDIX 4 HAQ-DI SCORING ALGORITHM

All language versions will use the following scoring system.

- There are four possible responses for each sub-category item, or component, within a category:

0 = without ANY difficulty	2 = with MUCH difficulty
1 = with SOME difficulty	3 = UNABLE to do
- Step 1: Calculate the maximum score for each of the 8 categories (7 of the categories are listed in the table below. The eighth category “Activities” is not listed in the table due to lack of questions regarding use of aids or device). At least one question in each category needs to be answered to compute the maximum score.
- If **an aid or device** is used or **help from another person** is needed, set the score for the associated category to the maximum score between 2 and the score in step 1.

Sub-domain	Aids or devices
Dressing&Grooming	Devices used for dressing (button hook, zipper pull, long-handled shoe horn, etc.)
Arising	Special or built up chair
Eating	Built up or special utensils
Walking	Cane, Walker, Crutches, Wheelchair
Hygiene	Raised toilet seat, Bathtub seat, Bathtub bar, Long-handled appliances in bathroom
Reach	Long-handled appliances for reach
Grip	Jar opener (for jars previously opened)

If no more than 2 categories have missing scores, then the disability score is the mean of the non-missing category scores. Otherwise, the disability score is set to missing.

Sponsor: Amgen Inc.

Statistical Analysis Plan

Protocol No: 20130108

10-December-2018/ Version 2.0

**APPENDIX 5 LIST OF EVENTS OF INTEREST AND THE ASSOCIATED SMQ AND EOI SEARCHING STRATEGIES**

Event of Interest	Category of EOI query (SMQ, Amgen query, or SOC)	Search Strategy	Additional Medical Review of the SMQ or SOC dataset for confirmation of the EOI
Infusion reactions including Hypersensitivity	Infusion reactions (Amgen query)	Broad*- TEAE with start date same as, or one day after, IP administration date	No
	Hypersensitivity (SMQ)	Broad- TEAE with start date same as, or one day after, IP administration date	No
Cardiac disorders	Cardiac disorders (SOC)		No
Serious infections	Infections and Infestations (SOC)	CTCAE grade >=3 or the serious TEAE	No
Progressive multifocal leukoencephalopathy	Progressive multifocal leukoencephalopathy (Amgen query)	Broad	Yes
Hematological reactions	Hematopoietic cytopenia (SMQ)	Broad	No
Hepatitis B reactivation	Hepatitis B Infection (Amgen query)	Broad	Yes
Opportunistic infections	Infections and infestations (SOC)		Yes
Hypogammaglobulinemia	Immune mediated events associated with oncologic immune therapies (Amgen query)	Broad	Yes

Sponsor: Amgen Inc.

Statistical Analysis Plan

Protocol No: 20130108

10-December-2018/ Version 2.0

Severe mucocutaneous reactions	Severe cutaneous adverse reactions (SMQ)	CTCAE grade >=3 or the serious TEAE, Broad search	No
Gastrointestinal perforation	Gastrointestinal perforation(SMQ)	Narrow	No

\*Broad search strategy includes both narrow scope terms and broad scope terms.

Sponsor: Amgen Inc.

Statistical Analysis Plan

Protocol No: 20130108

10-December-2018/ Version 2.0

---

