## 3. STUDY DESIGN

This is a randomized, double-blind, active-controlled 3-arm study in adult subjects with moderate to severe Rheumatoid Arthritis (RA) who have an inadequate response or intolerance to other disease-modifying anti-rheumatic drugs (DMARDs), which must include intolerance or inadequate response to one or more tumor necrosis factor (TNF) inhibitor therapies.

Sponsor: Amgen Inc.

Statistical Analysis Plan

Protocol No: 20130108

10-December-2018/ Version 2.0

---

Approximately 300 subjects (100 per treatment group) will be enrolled. The subjects will be randomized to receive either 2 IV infusions of ABP 798, 1000 mg each, given 2 weeks apart (treatment group A), or 2 IV infusions of rituximab (US) 1000 mg each, given 2 weeks apart (treatment group B) or 2 IV infusions of rituximab (EU), 1000 mg each, given 2 weeks apart (treatment group C) in a double blind fashion. A total of 2 doses will be administered during the study; each dose consists of 2 infusions, 2 weeks apart.

An independent data monitoring committee (DMC) will evaluate the safety data throughout the study, including an initial safety analysis after the first 18 subjects have received the first dose (1000 mg x 2 infusions of either ABP 798 or rituximab (EU) or rituximab (US)).

At week 24, the subjects in treatment groups A and C will continue with and receive the second dose of the same treatment, and the subjects in treatment group B will transition to treatment group A1 and receive ABP 798 1000 mg x 2 as their second dose.

Retreatment may occur earlier, i.e., anytime from week 16 to week 24, in individual subjects, if necessary in the opinion of the Investigator.

The end of study (EOS) will be at week 48 (or 24 weeks after the first infusion of second dose for subjects retreated before week 24), and a final analysis will be performed when all subjects have completed or have had the opportunity to complete the week 48/EOS assessments.

See [Figure 1](#) below for a summary of the study design.

[figure not shown]

Sponsor: Amgen Inc.

Statistical Analysis Plan

Protocol No: 20130108

10-December-2018/ Version 2.0

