## 5.4 SAFETY

### Adverse Event of Interest (AEOI)

An AEOI is defined as a noteworthy TEAE for a particular product or class of products that a sponsor may wish to monitor carefully. It could be serious or non-serious, and could include events that might be potential precursors or prodromes for more serious medical conditions in susceptible individuals (Council for International Organizations of Medical Sciences [CIOMS] VI, 2005). The AEOIs for this study will include:

- infusion reactions including hypersensitivity,
- cardiac disorders,
- serious infections,
- progressive multifocal leukoencephalopathy,
- hematological reactions,
- hepatitis B reaction,
- opportunistic infections
- hypogammaglobulinemia.
- severe mucocutaneous reactions,
- gastrointestinal perforation

Events of interest were identified using the latest versions of pre-specified Standardised MeDRA query (SMQ) where available. If no SMQ is available for use as a search tool for a given EOI (eg. Infusion reactions), a customized search strategy developed at Amgen or medical review will be used where SMQ is not available. [Appendix 5](#) provides the search strategy used to retrieve the events of interest. The preferred terms used in the searches are stored in a central PRA server location for analyses.

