### **Treatment-emergent Adverse Event**

A treatment-emergent AE (TEAE) is defined as an AE that begins or increases in severity or frequency at or after the first study IP administration through EOS. If the AE starts on the same day as the first dose of IP, then the flag indicating whether the AE started prior to the first dose on the adverse event CRF page will be used.

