### **9.8.1 Adverse Events**

All reported AEs will be coded to the appropriate SOC and PT according to the most current version of MedDRA, and the severity of each AE will be graded by the investigator per CTCAE v4.03 criteria.

Only TEAE will be tabulated.

Subject incidence of the following AEs will be tabulated by treatment groups and by SOC, PT, and maximum severity grade per CTCAE v4.03:

- treatment-emergent AEs

Subject incidence of the following AEs will be tabulated by treatment groups and by SOC and PT:

Sponsor: Amgen Inc.

Statistical Analysis Plan

Protocol No: 20130108

10-December-2018/ Version 2.0

- treatment-emergent AEs

Subject incidence of the following AEs will be tabulated by preferred term in descending order of frequency in the ABP798 column:

- treatment-emergent AEs
- grade 3 or higher treatment-emergent AEs
- treatment-emergent AEs leading to discontinuation of IP/study
- treatment-emergent AEs leading to infusion delay/infusion not given
- treatment-emergent AEOIs

For treatment-emergent AEOIs, the point estimate and 95% CI for RD of the subject incidence between ABP and the reference product are provided.

Exposure adjusted subject incidence rate (EAIR) of the following AEs will be tabulated by preferred term in descending order of frequency in the ABP798 column for the entire study:

- treatment-emergent AEs
- treatment-emergent AEOIs

The point estimate and 95% CI for RR of the EAIR between ABP and the reference product are also provided.

AEs leading to discontinuation of IP/study are those with an action taken with Investigational Medicinal Product of “dose discontinued” or those with other action taken of “discontinued from study”. If subjects have an AE for action taken with Investigational Medicinal Product of “dose delayed/not administered” checked, that AE leads to the infusion delay/infusion not given. If an AE leads to multiple actions taken with IP, only the last action will be captured in the eCRF.

Counting of AEs will be by subject, and subjects will be counted only once within each SOC or PT. For tables categorized by severity, subjects with multiple events within a particular SOC or preferred term will be counted under the category of their most severe event with that SOC or preferred term.

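### The only grouped hypersensitivity event of interest counts onsets on the infusion day or the next day; later hypersensitivity has no grouped comparison between arms

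*SAP*

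**What the plan says.** SAP 5.4 lists ten adverse events of interest. The only one that mentions hypersensitivity is "infusion reactions including hypersensitivity", and the section points to Appendix 5, which "provides the search strategy used to retrieve the events of interest".

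Appendix 5 gives that category two search rows, both broad in scope: a sponsor query for infusion reactions, and the Hypersensitivity SMQ. Each carries the same onset condition, "TEAE with start date same as, or one day after, IP administration date", and neither has additional medical review. No other row in Appendix 5 has an onset condition.

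SAP 9.8.1 sets the comparison: "For treatment-emergent AEOIs, the point estimate and 95% CI for RD of the subject incidence between ABP and the reference product are provided". It also gives exposure-adjusted incidence rates, with a rate ratio and 95% CI, for events of interest and for all treatment-emergent events by preferred term.

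Treatment-emergent events are those that begin or worsen "at or after the first study IP administration through EOS", so later reactions are collected. On the design, SAP section 3 says "each dose consists of 2 infusions, 2 weeks apart", with two doses in all. At week 24, "the subjects in treatment group B will transition to treatment group A1 and receive ABP 798 1000 mg x 2 as their second dose".

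**The concern.** A one-day window is a natural definition of an infusion reaction. Here it is also applied to the whole Hypersensitivity SMQ, and no second row picks up hypersensitivity of later onset. As general immunology, not stated in the documents, immune reactions to a protein drug can begin days to weeks after exposure.

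Comparing safety and immunogenicity with rituximab is a stated secondary objective, and the plan follows immunogenicity itself over weeks. Protocol 12.6.7.3 tabulates antibodies in the second-dose period to 4 weeks after its last infusion, and the SAP antibody visits run to week 48. The grouped clinical counterpart stops one day after each infusion.

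Hypersensitivity is coded under many preferred terms, which is the reason for using an SMQ. A modest imbalance in later reactions, including after the switch to ABP 798, could be spread over several preferred-term rows and be hard to see.

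**Working it through.** The documents state no figure that depends on this definition, so there is none to reproduce. The check is a reading of the rule and a count of days.

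**Inputs**
- Infusions: 2 doses of 2 infusions, two weeks apart (SAP section 3).
- Second dose: week 24, or as early as week 16 (SAP section 3).
- End of study: "The end of study (EOS) will be at week 48", or 24 weeks after the first infusion of the second dose if retreated early (SAP section 3).
- Eligible onset days: each infusion day and the day after (Appendix 5).

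**Formula.** Let R be the study day of the first infusion of the second dose. Infusions fall on days 1, 15, R and R + 14, and follow-up ends on day R + 168. Eligible days = 4 infusions × 2 days = 8, with 4 in each dose period.

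**Results**

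| Retreatment | Entire study | Before second dose | From second dose on |
|---|---|---|---|
| Week 24 (R = 169, end day 337) | 8/337 = 2.4% | 4/168 = 2.4% | 4/169 = 2.4% |
| Week 16 (R = 113, end day 281) | 8/281 = 2.8% | 4/112 = 3.6% | 4/169 = 2.4% |

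Without the window, or with it replaced by an onset split, all 337 days become eligible under the week-24 schedule, and all 169 in the second-dose period.

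**What the rule excludes.** Take an event coded to the Hypersensitivity SMQ with onset on day 10. The most recent infusion was on day 1, so the event fails the condition on both rows and does not enter this category. The same holds for onset on day 190, after infusions on days 169 and 183, when a subject randomized to rituximab (US) is receiving ABP 798. The one table that shows this category by infusion (Table 14-6.6.2.2.1) uses the same windowed events. No listed sensitivity analysis or table drops the window.

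**What the count does not show.** These are shares of calendar time. Reactions are not expected to be spread evenly over the study, and the documents give neither a hypersensitivity rate nor an onset distribution. The number of excluded events cannot be derived from them.

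**The case against.** The strongest reply is that the window fits its label. An infusion reaction is defined by its timing, the rule is the same in every arm and favors none, safety is descriptive, and no decision rests on this row. No document promises a later-onset category, so nothing is contradicted. Immunogenicity is also measured directly through binding and neutralizing antibodies. All of this stands, and it makes the point an improvement rather than an error.

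Four stronger readings are tempting, and the documents do not support them.

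- **Late hypersensitivity gets no confidence interval.** Each preferred term has an exposure-adjusted rate ratio with a 95% CI (SAP 9.8.1, Table 14-6.7.1). Only the grouped comparison is missing.
- **Late events survive only as scattered preferred terms.** They also appear by system organ class and by maximum grade. Separate tables cover grade 3 or higher events, serious events, events leading to discontinuation, and events leading to a delayed or omitted infusion.
- **A late difference shows as zero throughout the event-of-interest tables.** That is assured only for the windowed category. Rows with no onset condition could catch some late events, for example severe mucocutaneous reactions, although that row requires grade 3 or higher or a serious event.
- **About 98% of the information is lost.** The 2.4% counts days, not events.

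The thin post-switch reporting also has a separate cause. Protocol 12.6.7 describes summaries from the second dose to end of study, whereas SAP 9.8 generally reports only the first-dose period and the entire study. SAP section 10 does not list this among its changes. It affects every event of interest and is not a result of the onset window.

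**Conclusion.** The point holds as a gap in grouping. Under Appendix 5 as written, hypersensitivity starting two or more days after the most recent infusion is absent from the only grouped hypersensitivity count, risk difference and 95% CI, in the first-dose period and after the switch to ABP 798. This follows from the text and needs no assumption.

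Its practical weight rests on the outside premise that some relevant hypersensitivity starts later than one day after infusion, and its size in events is unknown. No primary or efficacy conclusion is affected. It is worth correcting because the data are already collected and coded and the correction is cheap.

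**What to change.** Keep the current infusion-reaction row in Appendix 5 unchanged. Add one supplementary row in either form:

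1. Hypersensitivity SMQ, narrow scope, any onset after first treatment; or
2. Hypersensitivity SMQ with onset split into day 0-1 and later, using the same scope in both parts so that the counts can be compared.

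Report the same risk difference and 95% CI as for the other events of interest. Do so for the first-dose period and for the second-dose period already described in Protocol 12.6.7, with subjects grouped by treatment sequence. Fix the definition before unblinding; if that is no longer possible, label the analysis post hoc.

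The cost is one more descriptive row. It needs no new data collection, sample size or alpha. The downside is that a few unrelated allergic events may be counted, which the narrow scope limits.
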